PI: [name]

IRB Study Number: 20200857

NCT04717466

Version 9, Date: 21Mar2024

1) Protocol Title

Brain morphological changes accompanied by effective biologic treatments for psoriasis and their associations with the improvement of well-being, itch, and pain

2) IRB Review History*

N/A

3) Objectives*

The purpose of this study is to assess the effect of a biologic drug targeting the IL-17 pathway (secukinumab) on brain plasticity and examine whether the plastic changes correlate with the improvement of perception of wellbeing, itch, and pain in patients with psoriasis.

4) Background*

Psoriasis is a chronic skin inflammatory disease, affecting 2 % of people in the US. Following Interleukin-17 (IL-17) neutralization, patients with psoriasis experience rapid changes in their well-being and mood. Though IL-17 neutralization-induced improvement in plaques and Psoriasis Area and Severity Index (PASI) score takes weeks, patients often state they feel significantly less pain and itch, and note improved mood after only one injection (Yosipovitch et al., 2019). It is currently unknown how IL-17 neutralization affects the improved perceptions of patients with psoriasis so rapidly as the drug does not cross the blood–brain barrier. Previous drug trials using DMARDS and TNF inhibitors for psoriatic and inflammatory joint disease have shown neuroplastic changes in the brain (Baliki et al. 2005, Harvey et al. 2012). The potent new generation of biologic drugs targeting IL-17 have more robust and rapid effect on psoriasis than the drugs mentioned above (Yosipovitch et al., 2019). Therefore, assessing the effect of these drugs on brain plasticity and correlating it to the improvement of itch, pain and perception of well-being is a timely topic to investigate.

The aim of this study is to elucidate brain mechanisms associated with perceptions of well-being and improvements in itch and/or pain after use of a potent effective treatment for psoriasis using IL-17 neutralization.

5) Inclusion and Exclusion Criteria*

Inclusion:

- 1) Between 18 and 65 years of age.
- 2) Psoriasis patients (with/without psoriatic arthritis): Psoriasis Area (BSA) is more than 5%.

PI: [name]

IRB Study Number: 20200857

NCT04717466

Version 9, Date: 21Mar2024

- 3) Psoriasis patietns must have had a TB test in the past 8 months (if a patient has not had one, the study will provide one).
- 4) Healthy subjects: in general, good health without history of neurological and psychiatric diseases. No chronic itch, pain, skin or systemic conditions currently or in the past.
- 5) Women of child bearing potential will be administered a pregnancy test to verify that they are not pregnant.
- 6) MRI Compatibility: No major contraindication for MRI (pacemaker, vascular stents, metallic ear tubes, and absence of metal implants or braces) as assessed by MRI technologist using site approved screening form.
- 7) Participants have to be able to speak and read English fluently.
- 8) Participants must have signed a written informed consent before being enrolled in the study

Exclusion:

- 1) Individuals under 18 or over 65 years of age.
- 2) Inability to complete the required measures.
- 3) Participants who use antihistamine drugs for itch relief
- 4) Suffering from any disease state or physical condition, which would increase their health risk by study participation.
- 5) Patients with chronic infectious diseases (e.g., mycobacterial and fungal infections and chronic tuberculosis) or inflammatory bowel disease.
- 6) Patients without a negative TB test in the past 12 months.
- 7) Hypersensitivity or anaphylaxis to biologics
- 8) Patients with treatment of biologics should not receive live vaccines. Thus, age appropriate immunizations according to current immunization guidelines must be completed before the experiment.
- 9) Patients with primary immunodeficiet lacking IL-17, patinets with autoantibiobodies against IL-17
- 10) Currently enrolled in any investigational study in which the subject is receiving any type of drug, biological, or non-drug therapy.
- 11) Recent initiation (within last 3 months) or change in dose of centrally acting agents such as antidepressants, neuroleptics or neuropathic medications.
- 12) Patients who were previously treated with drugs targeting IL-17
- 13) Patients who have used biologics in the past in the past 8 weeks or Otezla in the past 4 weeks.

PI: [name]

IRB Study Number: 20200857

NCT04717466

Version 9, Date: 21Mar2024

- 14) Patients who use centrally acting agents only when they need. The purpose is to avoid a risk of acute effect of these agents on brain activity.
- 15) Current treatment with opioid analgesics.
- 16) Uncontrolled thyroid disease.
- 17) Use of illicit drugs or history of opiate addiction.
- 18) Diagnosis of a major psychiatric disorder such as schizophrenia, major depression or bipolar disorder that is active currently.
- 19) Morbid obesity
- 20) Weight: 250 lb or more
- 21) Any known diseases or disorders that may affect conducting the experiments (e.g., intracranial pathology, claustrophobia, severe respiratory or cardiovascular problems, active fibromyalgia) or diseases that have potential risks of infections (e.g., HIV, Hepatitis C, etc).
- 22) Inability to speak and read English.
- 23) Pregnant.
- 24) Incarcerated.

6) Number of Subjects*

This is an exploratory study to elucidate brain mechanisms associated with perceptions of well-being and improvements in itch and/or pain after use of a potent effective treatment for psoriasis using IL-17 neutralization. We will enroll 15 psoriasis patients and 15 healthy subjects with an approximately equal gender distribution, in order for 10 psoriasis patients and 10 healthy subjects to complete the study.

Psoriasis patients will be recruited from the Department of Dermatology Clinics. An approximately equal number of men and women between 18 and 65 years of age will be recruited using IRB-approved advertising. All participants will be required to consent and to fulfill the inclusion and exclusion criteria. Healthy subjects (similar age and gender ratio to the patient group) will be recruited through IRB-approved advertisement. UM students or employees may be enrolled in this study as long as they fulfill the inclusion and exclusion criteria.

7) Recruitment Methods*

Patients seen for their routine care at the Dermatology Outpatient Clinics at the University of Miami Hospital, South Miami satellite site, and Lennar Medical Foundation satellite site will be identified for possible study eligibility by any of the dermatologists in our practice. If the treating dermatologist is a study team member, they will ask the potential subject if they would be interested in being contacted by the study team to learn

PI: [name]

IRB Study Number: 20200857

NCT04717466

Version 9, Date: 21Mar2024

more about a research study on chronic itch. A partial HIPAA waiver is needed, so that if the patient gives permission to be contacted, they will then be approached by a member of the study team while they are in clinic or if that is not feasible then the treating dermatologist will ask if the patient would like to be contacted by telephone. If the treating dermatologist is not a study team member, they will ask the potential subject to contact the study team for more information by providing the study team's contact information and/or the study flyer. If it is then determined that they are interested in participating, they will be scheduled for a visit at our research site where informed consent and all other study procedures will take place. The risks/benefits of the study will be presented to the subjects, as well as the disclaimer that refusal to participate in the study will in no way, shape, or form alter the type or quality of their care.

Patients with the diagnosis of psoriasis who sign the University of Miami's Consent to Contact consent during their routine medical care will be identified using research IT and URIDE. Each of those individuals will then be contacted by phone by a study team member and asked if they would be interested in learning more about a research study for psoriasis (see phone script). If they are interested in participating, they will be scheduled for a visit at our dermatology clinical research site where informed consent and all other study procedures will take place. The risks/benefits of the study will be presented to the subjects, as well as the disclaimer that refusal to participate in the study will in no way, shape, or form alter the type or quality of their care.

Furthermore, using the approved flyer, we will announce this study on the Facebook page of the University of Miami Department of Dermatology and Cutaneous Surgery to recruit patients and healthy subjects. Emails of the approved flyer will also be sent to the Miami Society for Dermatology and Cutaneous Surgery list serve and Palm Beach County Society for Dermatology list serve to inform community clinicians about this study. We will also post fliers at designated locations throughout University of Miami buildings and in our dermatology clinics for recruiting patients and healthy subjects.

For recruitment purposes, we will advertise our study through the national psoriasis foundation and social media to distribute study advertisement.

PI: [name]

IRB Study Number: 20200857

NCT04717466

Version 9, Date: 21Mar2024

8) Study Timelines*

This project is expected to last 24 months. There will be 3-4 study visits and 1 follow up visit for psoriasis patients and 3 study visits for healthy subjects. Each study visit will last approximately 2 hours.

9) Study Endpoints*

The primary endpoints:

Identify changes in brain anatomy (gray matter density) in psoriasis patients after injection of Sucukinumab using use voxel-based morphmetory (VBM) between baseline, 1 week (visit 2), and 4 weeks (visit 3) as well as by comaparing between the patient and healthy control group.

Identify changes in baseline brain activity in psoriasis patients after injection of Secukinumab using and arterla spin labeling MRI (ASL) between baseline, 1 week (visit 2), and 4 weeks (visit 3) as well as by comaparing between the patient and healthy control group.

The secondary endpoints:

Assessment of how an effective biologic treatment of psoriasis (Secukinumab) improves itch by using a Numerical Rating Scaling (NRS) ranging from 0 (no itch) to 10 (the worst itch imaginable) to assess severity of itch between baseline, 1 week (visit 2), and 4 weeks (visit 3) as well as by comaparing between the patient and healthy control group.

Assessment of how an effective biologic treatment of psoriasis (Secukinumab) improves pain by using a Numerical Rating Scaling (NRS) ranging from 0 (no pain) to 10 (the worst pain imaginable) to assess severity of itch between baseline, 1 week (visit 2), and 4 weeks (visit 3) as well as by comaparing between the patient and healthy control group.

Assessment of how an effective biologic treatment of psoriasis (Secukinumab) improves severity of psoriasis by using the Psoriasis Area and Severity Index (PASI) to assess severity of psoriasis ranging from 0 to 100, with a higher score indicating more severe psoriasis between baseline, 1 week (visit 2), and 4 weeks (visit 3) as well as by comaparing between the patient and healthy control group.

Assessment of how an effective biologic treatment of psoriasis (Secukinumab) improves the patient's well-being by using the 5-item World Health Organization Well-Being Index (WHO-5) ranging from 0 to 25 with a higher score indicating better well-being between baseline, 1

PI: [name]

IRB Study Number: 20200857

NCT04717466

Version 9, Date: 21Mar2024

week (visit 2), and 4 weeks (visit 3) as well as by comaparing between the patient and healthy control group.

Assessment of how an effective biologic treatment of psoriasis (Secukinumab) improves the patient's quality of sleep by using the Numerical Rating Scaling (NRS) rainging from 0 to 10, with a higher score indicating lower sleep quality between baseline, 1 week (visit 2), and 4 weeks (visit 3) as well as by comaparing between the patient and healthy control group.

Assessment of how an effective biologic treatment of psoriasis (Secukinumab) improves the patient's physical activity by using the 7-days physical activity recall (7D-PAR) ranging from 0 to 27, with a higher score indicating more physical activity between baseline, 1 week (visit 2), and 4 weeks (visit 3) as well as by comaparing between the patient and healthy control group.

Assessment of how an effective biologic treatment of psoriasis (Secukinumab) improves stress in daily life in psoriasis patients by using the Perceived Stress Questionnaire (PSQ) ranging from 0 to 1, with a higher score indicating more stress between baseline, 1 week (visit 2), and 4 weeks (visit 3) as well as by comaparing between the patient and healthy control group.

10) Schedule of Assessments

10 patients with psoriasis and 10 healthy controls will participate in this study. The patient group will have 3-4 study visits and 1 follow up visit, while the healthy control group will have 3 study visits (Fig. 1). Patients can be rescreened in a washout period is needed.

Pre-Study visit (Patients only)

- *Patients that have not had a TB preformed in the past 8 months will have to attend this pre-study visit to undergo a TB test
 - Patients will fill out an informed consent
 - Assessment of Body Surface Area (BSA) to show percent of psosiais involvement from 0 to 100%.
 - Blood (~4ml) will be drawn for the Quantiferon TB Gold test
 - Subjects can not proceed to the 1st study baseline visit until results are received

PI: [name]

IRB Study Number: 20200857

NCT04717466

Version 9, Date: 21Mar2024

- If an indeterminate result is received, the subject will be offered to repeat the test once
- If a positive result is received, the subject will be excluded from the study and refered to their primary care physician for further assessment and/or treatment
- If a negative result is received, the subject may continue with the study

1st study visit (Baseline measurements)

- All participants will be asked to fill out an informed consent (if not completed at the prestudy visit), and a form for demographic information including health information. Medical history and current medications will be documented from medical records chart review. Females of childbearing potential will undergo an hCG pregnancy test.
- MRI measurments of brain anatomy and activity using voxel-based morphmetory (VBM) and arterial spin labeling (ASL). MRIs in the study do not involve the use of contrast for all study visits.
- -Assessment of Body Surface Area (BSA) to show percent of psosiais involvement from 0 to 100%.
- Assessment of severity of itch and pain using numerical rating scale (NRS) ranging from 0 (no itch/pain) to 10 (the worst itch/pain imaginable).
- Assessment of wellbeing using The 5-item World Health Organization Well-Being Index (WHO-5) (Topp et al., 2018)
- Assessment of severity of psoriasis using Psoriasis Area and Severity Index (PASI) (Fredriksson and Pettersson, 1978)
- Assessment of the quality of sleep using the sleep NRS- Assessment of excerise using 7-days physical activity recall (7D-PAR) (Young et al., 2013).
- Assessment of stress using Perceived Stress Questionnaire (PSQ) (Levenstein et al., 1993).
- At the end of the above measurements and assessments, injection of Secukinumab to psoriasis patients. That is, 2 Sensoready pens, dose: 150 mg/ml per pen, will be applied to different locations (i.e., 150 mg/ml x 2). A medically qualified study team member will explain how to do the injection and patients will inject by themselves in front of the study team member.
- *: Healthy controls will perform only VBM and ASL measurements, WHO-5, Sleep-NRS, 7D-PAR and PSQ. No injections will be performed to healthy controls.

[figure not shown]
PI: [name]

IRB Study Number: 20200857

NCT04717466

Version 9, Date: 21Mar2024

Fig. Time course of experiment for each participant

Injection of Secukinumab at home every 4 weeks (Only Patients)

2nd study visit (1 week (± 3 days) after the initial injection of Sucukinumab)

- hCG pregnancy test
- MRI measurements of brain anatomy and activity using VBM and ASL.
- Assessment of severity of current itch and pain using NRS
- Assessment of wellbeing using WHO-5
- Assessment of severity of psoriasis using PASI
- Assessment of the quality of sleep using the sleep NRS
- Assessment of excersise using 7D-PAR
- Assessment of stress using PSQ
- At the end of the above measurements and assessments, injection of Secukinumab to psoriasis patients (Patients will inject by themselves) (150 mg/ml x 2).
- *: Healthy Controls will perform only VBM and ASL measurements, WHO-5, Sleep-NRS, 7D-PAR and PSQ. No injections will be performed to healthy controls

Between 2nd and 3rd study visits

Psoriasis patients will inject Secukinumab (150 mg/ml x 2) once a week (\pm 2 days) at home for 2 weeks (i.e., twice before the third study visit). Study staff will confirm whether patients have injected by phone call or email.

3rd study visit (4 weeks (± 3 days) after the initial injection of Sucuknumab)

- hCG pregnancy test
- MRI measurements of brain anatomy and activity using VBM and ASL.
- Assessment of severity of current itch and pain using NRS
- Assessment of wellbeing using WHO-5
- Assessment of severity of psoriasis using PASI
- Assessment of the quality of sleep using the sleep NRS
- Assessment of exercise using 7D-PAR
- Assessment of stress using PSQ

PI: [name]

IRB Study Number: 20200857

NCT04717466

Version 9, Date: 21Mar2024

- At the end of the above measurements and assessments, injection of Secukinumab to psoriasis patients (Patients will inject by themselves) (150 mg/ml x 2).

*: Healthy controls will perform only VBM and ASL measurements, WHO-5, Sleep-NRS, 7D-PAR and PSQ.

Between 3rd study visit and Follow up visit

After the 3rd study visits, psoriasis patients will continue injections of Secukinumab until the follow up visit (3 months after the 3rd study visit). However, the interval of injection will be changed from 1 week (\pm 2 days) to 4 weeks. That is, patients will inject (150 mg/ml x 2) every 4 weeks before the follow-up visit (i.e., twice before the follow-up visit).. Study staff will confirm whether patients have injected by phone call or email.

Follow up visit ONLY for patients (3 months (\pm 3 days) after the 3rd study visit)

- hCG pregnancy test
- MRI measurements of brain anatomy and activity using VBM and ASL.
- Assessment of wellbeing using WHO-5
- Assessment of severity of current itch and pain using NRS
- Assessment of severity of psoriasis using PASI
- Assessment of the quality of sleep using the sleep NRS
- Assessment of excersise using 7D-PAR
- Assessment of stress using PSQ

11) Data Management*

Data analysis

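### The 4-week injection interval, the 3-month gap to follow-up and the count of two injections agree only if 3 months means 12 weeks

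*Combined protocol and SAP*

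**What the plan says.** Four statements in section 10 (Schedule of Assessments) bear on this.

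- Visit 3 ends with an injection: "At the end of the above measurements and assessments, injection of Secukinumab to psoriasis patients (Patients will inject by themselves) (150 mg/ml x 2").
- After visit 3, patients "will continue injections of Secukinumab until the follow up visit (3 months after the 3rd study visit").
- The interval lengthens from weekly to 4-weekly, and the text glosses the result as "every 4 weeks before the follow-up visit (i.e., twice before the follow-up visit").
- The next visit is headed "Follow up visit ONLY for patients (3 months", with a window of ± 3 days. Its list of procedures covers the pregnancy test, MRI and rating scales. It contains no injection.

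The weekly interval carries a tolerance of ± 2 days; the 4-week interval carries none. Staff are to confirm by phone or email that patients have injected, but the text does not expressly ask for the date.

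Section 11 (Data analysis) compares the follow-up MRI and clinical scales with visit 1 in patients, and correlates brain and clinical changes over all visits. Section 9 (Study Endpoints) names only baseline, 1 week and 4 weeks.

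**The concern.** An interval, a duration and a count are given for the same period, and any two of them fix the third. If they disagree, whoever instructs the patient has to choose which to follow. Following the count gives one number of injections before the follow-up scan; following the interval may give one more.

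The number of injections and the time since the last one describe drug exposure at the follow-up scan, and that scan is analysed. Section 6 aims for 10 patients to complete, so even a few patients handled differently would be a sizeable share of the follow-up data.

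**Working it through.** **Inputs.** All are from section 10 except the length of a calendar month, which is ordinary calendar arithmetic and not stated in the protocol.

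- Day 0: the injection at the end of visit 3.
- Interval: 4 weeks = 28 days.
- Follow-up: 3 months ± 3 days after visit 3.
- Stated count: 2.

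**Due dates.** 28 × 1 = 28, 28 × 2 = 56, 28 × 3 = 84.

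**Can the stated count be reproduced?** Count the due dates that fall before the visit.

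| Reading of 3 months | Nominal day | Window (± 3 days) | Due before the visit |
|---|---|---|---|
| 12 weeks | 84 | 81 to 87 | two if the visit is on days 81 to 84; three if on days 85 to 87 |
| 13 weeks | 91 | 88 to 94 | three throughout |
| Calendar months | 89 to 92 | 86 to 95 | three throughout |

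The calendar range runs from 28 + 31 + 30 = 89 days (February to April) to 31 + 31 + 30 = 92 days (July to September). The stated two is reproduced only on the 12-week reading with a visit no later than day 84. The third injection then falls due on the visit day or up to 84 − 81 = 3 days after the visit.

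**Total injections.** Through visit 3 there are five: visit 1, visit 2, two at home, and visit 3. Adding two gives 5 + 2 = 7; adding three gives 5 + 3 = 8.

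**Days from last injection to follow-up scan.**

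- Calendar months, two injections (last on day 56): 86 − 56 = 30 to 95 − 56 = 39.
- Calendar months, three injections (last on day 84): 86 − 84 = 2 to 95 − 84 = 11.
- 12 weeks, two injections: 81 − 56 = 25 to 87 − 56 = 31.

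Against the 28-day interval, two injections on the calendar reading put the scan 30 − 28 = 2 to 39 − 28 = 11 days beyond it. On the 12-week reading the scan lies between 28 − 25 = 3 days short of the interval and 31 − 28 = 3 days beyond it.

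**The case against.** The best defence is that 3 months is shorthand for three 4-week cycles. The injections before follow-up are then on days 28 and 56, which is two, with the next due on the nominal visit day. The weekly phase is counted in just this way: patients inject "at home for 2 weeks (i.e., twice before the third study visit"), on days 14 and 21, and the next injection is given at visit 3 on day 28. Because injections are said to continue until the follow-up visit, ending treatment there would also explain why none is listed at it. The time-course figure is not available in the text reviewed and might show the gap in weeks.

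This stands as a possible reading, but it does not settle the text. The protocol gives the earlier visits in weeks and this one in months, and nothing equates the two. Even at 12 weeks, a visit on days 85 to 87 is inside the window and comes after the third due date. The parallel with the weekly phase is also incomplete, because visit 3 lists the next injection and the follow-up visit does not.

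The objection does rule out several stronger readings that a reader might infer:

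- **Exposure at follow-up is undefined.** It is not. The text states a count, and the alternatives are bounded at two or three injections. The staff contacts should also show how many were taken, if not when.
- **Two patients could both comply and still differ.** On the calendar reading neither complies with the whole text: two injections depart from the interval and three depart from the count.
- **The 3-month result mixes continued with lapsed treatment.** Nothing in the documents shows that a few days beyond 4 weeks matters for gray matter density or ASL.
- **The primary or secondary endpoints are compromised.** Their time points all come before this phase begins.

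**Conclusion.** The maintenance schedule is inconsistent as written unless 3 months is taken as 12 weeks. On the calendar reading the discrepancy is one injection (three due, two stated) at every point in the visit window. On the 12-week reading the count holds for visits up to day 84 and fails for days 85 to 87. Exposure at the follow-up scan is therefore ambiguous within known bounds.

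The conclusion rests on taking the visit 3 injection as day 0 and on an exact 28-day interval, since no tolerance is given for it. The effect is confined to the follow-up comparison with visit 1 and the all-visit correlations in patients. Its direction and size on the scans cannot be derived from the documents. It merits correction because the follow-up data are analysed and the conflicting figures set exposure at that scan, but it does not threaten the baseline, 1-week or 4-week results.

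**What to change.** The sponsor and investigator should reconcile the interval, the number of injections and the follow-up timing. Which schedule is right is for them to decide. The amended text should:

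- give the follow-up visit in days or weeks from visit 3, with its window;
- give an injection count that matches the interval across that whole window, and say what happens to an injection falling due on or near the visit day;
- have staff record the date of the last injection before each scan, as part of the confirmation contacts already planned.

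For patients who have already passed this phase, the number and, where recoverable, the dates of maintenance injections should be reported with the follow-up results. The cost is one wording amendment and one recorded date per scan, with no extra patients, visits or procedures.
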